9.3. Storage and Stability

PHA-848125AC is to be stored under refrigerated conditions (5 \pm 3 °C; 36-46 °F) and in the original packaging, out of the reach and sight of children.

To ensure optimal environmental and patient exposure protection, the packaging has been designed as a single use one.

On the basis of the available supportive stability results, a provisional shelf-life of 48 months is assigned to both 50 mg and 100 mg capsules, when stored at 5 ± 3 °C (36-46 °F) in the original packaging.

Concurrent stability studies on the clinical batches of the current formulation will be carried out in order to evaluate the chemical and physical parameters, and the expiry date will be extended accordingly with the stability results. Any unexpected finding will be promptly communicated to the investigators and to the Health Authorities.

9.3.1. Source of Drug

NerPharMa (NMS Group), on behalf of the Sponsor Tiziana Life Sciences PLC will supply PHA-848125AC (milciclib maleate) free of charge. Additional supply may be obtained by contacting CLIOSS (see Study Manual for contact information).

9.3.2. Drug Accountability

PHA-848125AC must not be used outside the context of this protocol. Under no circumstances should the Investigator or site personnel supply study product to other Investigators or clinics, or allow the supplies to be used other than as directed by this protocol without prior authorization from the Sponsor.

Adequate records on receipt, use, return, loss, or other disposition of medication must be maintained. A specific drug accountability form supplied by the Sponsor or computer records used by the pharmacy at the investigational site, can be used to provide drug accountability information. In either case, information describing study drug supplies and

Tiziana Life Sciences, PLC - Confidential Page 47 of 101

Milciclib maleate (PHA-848125AC)	CDKO-125a-006-P4
Protocol for Study CDKO-125a-006	09 March 2017

their disposition, subject by subject, must be provided, signed by the Investigator (or the pharmacist or other person who dispensed the drug) and collected by the study monitor. Requisite data includes relevant dates, quantities, batches or code numbers, and subject identification for subjects who received study drug.

At the end of the study and upon authorization of the Sponsor, the study drug may be destroyed at the site as dictated by the appropriate standard procedures of the participating institutions. Destruction must be documented. Alternatively, all unused product will be collected by the local monitor and returned to NerPharMa.

If disposed locally, all used bottles and containers of study product should be discarded according to the standard institutional policy.

Study drug handling and accountability after the cut-off date of 31 May 2017 should continue as described above.

9.4. Treatment Administration

9.4.1. Treatment Dose and Schedule

PHA-848125AC will be administered orally at the dose of 150 mg/day (flat dose) once daily for 7 consecutive days of each treatment cycle. A treatment cycle will comprise 7 days of PHA-848125AC administration (Day 1 to 7) followed by 7 days of rest for a total of 14 days (2 weeks) period.

After an overnight fasting, with free access to water, patients will take the study drug with a large glass of plain water without ice. A light breakfast can be served 1.5-2 hours after study drug intake.

9.4.2. Duration of Treatment

Each patient will remain on treatment until disease progression, patient refusal, consent withdrawal, or the occurrence of unacceptable toxicity or of any other criteria for withdrawal as detailed in Section 10.

At the end of the treatment period, all patients will be followed for survival every 6 months up to 2 years after the end of treatment. Anyhow, if a patient stops the treatment before any documentation of PD, the follow up will be initially performed at 6-week intervals and will include a complete oncological assessment up to documentation of PD or the start of another antitumor therapy, then it will be continued for survival only every 6 months.

Patients still on treatment after the cut-off date of 30 April 2017, will be managed according to Section 9.5.

Tiziana Life Sciences, PLC - Confidential Page 48 of 101

9.4.3. Dose Modifications

Dose modifications may occur as a consequence of drug-related toxicities, during a cycle or at the start of a new cycle. In the event of multiple toxicities, dose modifications should be applied based upon the most severe toxicity observed and attributable to PHA-848125AC.

As far as dose reductions are concerned, a dose reduction to the dose level of 100 mg/day (i.e. -33%) is recommended in case of poor tolerability of the full dose of 150 mg/day.

The dose of 100 mg/day (mean Day 7 AUC 19.9 μ M·h) was successfully used for 20 cycles in keeping disease control in a patient with colorectal cancer, initially treated at 150 mg/day for 7 cycles in the CDKO-125a-001 study.

Doses reduced for drug-related toxicity should not be re-escalated. Any exception is to be discussed between the Investigator and the Sponsor.

Table 4 describes the recommended dose modifications during the treatment cycles and at the start of any new cycle.

Note: the dose adjustments in the third column are intended as referred to the dose of Day 1 of the previous cycle.

Toxicity (Graded as per NCI CTCAE Criteria, Version 3.0)	During Treatment Cycle	Dose Adjustment for Next Treatment Cycle (after recovery from toxicities to grade ≤1, or to baseline values) ¶	
Hematologic			
Grade 0 or Grade 1	Maintain dose level	Maintain dose level	
Grade 2 Neutropenia (ANC < 1500-1000/mm ³) and/or Grade 2 Thrombocytopenia (platelet	If occurs during treatment, maintain daily dose level	Maintain dose level	
count <75000-50000/mm3)	Monitor until resolved to grade ≤ 1		
Grade 3 Neutropenia (ANC <1000-500/mm ³)	If occurs during treatment, decrease daily dose by one dose level Monitor until resolved to grade ≤1	Maintain dose level	
Grade 3 Thrombocytopenia (platelet count <50000-25000/mm3), uncomplicated or lasting less than 5 days	If occurs during treatment, decrease daily dose by one dose level Monitor until resolved to grade ≤1	Maintain dose level	
Grade 4 Neutropenia (ANC < 1000/mm³) lasting < 7 days	If occurs during treatment, decrease the daily dose by one dose level Monitor until resolved to grade ≤1	Maintain dose level	
Grade 4 Neutropenia (ANC < 1000/mm ³) lasting 7 days or more			
Febrile neutropenia (ANC <1,000/mm3 and fever of unknown origin ≥38.5°C)			
Neutropenic infection: grade \geq 3 (i.e. infection documented clinically or microbiologically with grade 3 or grade 4 neutropenia)	If occurs during treatment, interrupt the treatment Monitor until resolved to grade ≤1	\downarrow 1 dose level	
$\label{eq:Grade} \begin{array}{l} \mbox{Grade} \geq 3 \mbox{Thrombocytopenia} \ (\mbox{platelet count} < 50000/mm^3) \ \mbox{uncomplicated} \ \mbox{lasting 5 days or} \\ \mbox{more, or associated with bleeding and/or} \\ \mbox{requiring transfusion} \end{array}$			
Any other grade 4 hematological toxicity			
Nausea and/or Vomiting			
Grade 1 or 2 in absence of antiemetics	If occurs during treatment, maintain daily dose level and add antiemetics, if needed. If occurs during rest period, add antiemetics, if needed	Maintain dose level with antiemetics §, if needed	
Grade 3 in absence of antiemetics	If occurs during treatment, decrease the daily dose by one dose level, add antiemetics. If occurs during rest period, add antiemetics Monitor until resolved to grade ≤1	Maintain dose level with antiemetics §	
Grade \ge 3 in presence of antiemetics §	If occurs during treatment, interrupt treatment Monitor until resolved to grade ≤1	↓ 1 dose level	

Table 4. Criteria for PHA-848125AC Dose Modifications

Tiziana Life Sciences, PLC - Confidential Page 50 of 101

Toxicity (Graded as per NCI CTCAE Criteria, Version 3.0)	During Treatment Cycle	Dose Adjustment for Next Treatment Cycle (after recovery from toxicities to grade ≤1, or to baseline values) ¶
Diarrhea		
Grade 1 or 2 (in absence or presence of management of the event §)	If occurs during treatment, maintain daily dose level, add/adjust antidiarrheal treatment, if needed. If occurs during rest period, add/adjust antidiarrheal treatment, if needed	Maintain dose level
Grade \ge 3 despite optimal management of the event §	If occurs during treatment, interrupt treatment Monitor until resolved to grade ≤1	↓ 1 dose level
Neurologic		•
Grade 0, 1 or no worsening compared to baseline	Maintain dose level	Maintain dose level
Grade 2 tremors	If occurs during treatment, interrupt treatment	↓ 1 dose level or discontinue study treatment (Investigator to discuss with the Sponsor)
Grade > 2 tremors or any other Grade ≥ 2 neurological toxicity	Discontinue study treatment (Investigator to discuss with the Sponsor)	Discontinue study treatment (Investigator to discuss with the Sponsor)
Ocular/Visual		
Grade 0	Maintain dose level	Maintain dose level
Increase of 1 or more grades retinopathy by ophthalmologic examination compared to baseline	Discontinue study treatment	Discontinue study treatment
Other non hematological toxicity (except alop	ecia)	
Grade 0, 1	Maintain dose level	Maintain dose level
Grade 2	If occurs during treatment, maintain or decrease the daily dose by 1 dose level, if clinically indicated Monitor until resolved to grade ≤1	Maintain dose level
Grade ≥ 3	If occurs during treatment, interrupt treatment Monitor until resolved to grade ≤1	↓ 1 dose level
Failure to recover		
Failure to recover to grade \leq 1 toxicity (except alopecia) or to baseline values, if grade 2 is allowed at study entry, after delaying the initiation of next cycle by > 2 weeks	Monitor until resolved to grade ≤1	\downarrow 1 dose level (Investigator to discuss with the Sponsor)
\P : the dose adjustments in the third column are in	ntended as referred to the dose of Day	1 of the previous cycle.
§ For prophylaxis and management of the events Abbreviations: ANC = absolute neutrophil count National Cancer Institute	s, see Concomitant Medications and Ot ; CTCAE = Common Terminology Crite	her Therapy, Section 9.4.9. ria for Adverse Events, NCI =

Tiziana Life Sciences, PLC - Confidential Page 51 of 101

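### Section 9.4.3 contradicts itself on the next-cycle dose after a mid-cycle toxicity reduction: the no-re-escalation sentence and the Table 4 note give different doses

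*Protocol*

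**What the plan says.** Protocol Section 9.4.3 opens by placing reductions within a cycle in scope: "Dose modifications may occur as a consequence of drug-related toxicities, during a cycle or at the start of a new cycle". It gives 100 mg/day as the reduced level from 150 mg/day. It then sets a general rule, "Doses reduced for drug-related toxicity should not be re-escalated", followed by "Any exception is to be discussed between the Investigator and the Sponsor".

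The note before Table 4 fixes the reference dose for the next-cycle column: "the dose adjustments in the third column are intended as referred to the dose of Day 1 of the previous cycle". Footnote ¶ under the table repeats this.

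The affected rows of Table 4 are:

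- **Grade 3 neutropenia**, and **Grade 3 thrombocytopenia that is uncomplicated or lasts under 5 days**: "If occurs during treatment, decrease daily dose by one dose level".
- **Grade 4 neutropenia lasting under 7 days**: the same one-level cut.
- **Grade 3 nausea or vomiting without antiemetics**: "If occurs during treatment, decrease the daily dose by one dose level, add antiemetics".
- **Other Grade 2 non-hematological toxicity**: "If occurs during treatment, maintain or decrease the daily dose by 1 dose level, if clinically indicated".

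In all five rows the next-cycle column keeps the dose level (with antiemetics in the nausea/vomiting row). None of the five mentions the Sponsor.

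**The concern.** The table's note looks back past the mid-cycle cut to the Day 1 dose, so keeping the dose level means returning to the dose in force before the reduction. The general sentence says a dose reduced for drug-related toxicity is not raised again unless the exception has been discussed. Both apply to the same patient, and the protocol does not say which takes precedence.

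At stake is consistent dosing across sites in patients who have just had a drug-related toxicity. The dose intensity summaries in Section 12.3.3 would also be affected, because they would mix two dosing rules. A further consequence for the primary analysis set is possible, but it depends on how the 80% drug criterion in Section 12.2 is measured.

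**Working it through.** **Inputs.** Full dose 150 mg/day for 7 days per cycle (Section 9.4.1). Reduced level 100 mg/day, stated as -33% (Section 9.4.3). Evaluability threshold of 80% of drug over the first two cycles (Section 12.2). Mean Day 7 AUC from Table 1.

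**The plan's own figure.** (150 - 100)/150 = 33.3%, which matches the stated -33%.

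**Next-cycle dose.** Take a patient on 150 mg/day on Day 1 who is cut to 100 mg/day before Day 7 under one of the five rows.

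- Table 4 with its note: reference dose = Day 1 dose = 150 mg/day; level kept, so the next cycle is 150 mg/day.
- General sentence: the dose was reduced to 100 mg/day for drug-related toxicity and is not raised, so the next cycle is 100 mg/day.

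The gap is 50 mg/day, or 7 x 50 = 350 mg over the cycle. In Table 1 the mean Day 7 AUC is 25.3 ± 8.54 µM·h at 150 mg/day and 19.9 ± 10.5 µM·h at 100 mg/day, n = 6 each. The ratio of means is 25.3/19.9 = 1.27.

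**Which rows conflict.** Only rows pairing a mid-cycle cut with an unchanged next-cycle level do so. Rows that interrupt treatment and then go down one level, and rows that discontinue, are consistent with the general sentence.

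**Share of planned drug over cycles 1 and 2.** This assumes the criterion is counted in mg against full planned drug, 2 x 7 x 150 = 2 x 1050 = 2100 mg. For a cut starting on Day d of cycle 1:

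- cycle 1 drug = 150(d - 1) + 100(8 - d) mg
- cycle 2 drug = 1050 mg (Table 4 with note) or 700 mg (general sentence)
- share = (cycle 1 + cycle 2)/2100

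| Cut starts on Day | Cycle 1 (mg) | Share, Table 4 with note | Share, general sentence |
|---|---|---|---|
| 2 | 750 | 85.7% | 69.0% |
| 3 | 800 | 88.1% | 71.4% |
| 4 | 850 | 90.5% | 73.8% |
| 5 | 900 | 92.9% | 76.2% |
| 6 | 950 | 95.2% | 78.6% |
| 7 | 1000 | 97.6% | 81.0% |

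On that assumption, a cut starting on Days 2-6 leaves the patient above 80% under one rule and below it under the other. A Day 7 cut passes under both. If the criterion counts daily doses taken, or measures drug against the dose prescribed at the time, the rules do not differ and evaluability is unaffected.

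**The case against.** The strongest reply is that the protocol does give a specific answer. The note and footnote ¶ exist to say what the next-cycle column refers to, and Section 9.4.4 sends sites to Table 4. A workable reading is that within-cycle cuts are temporary, while reductions ordered in the next-cycle column persist. This is plausible, but it is written nowhere: the general sentence has no such limit, and the section's opening counts changes during a cycle as dose modifications. Nor can the five rows pass as the discussed exceptions. Where Sponsor discussion is intended, Table 4 says so, as in the tremor and other neurologic rows and the failure-to-recover row.

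The reply does limit how far the point goes. A reader might infer that sites will dose the same patient differently. The documents support only that they may: the table gives a usable answer, its modifications are described as recommended, and the exception clause offers a route to the Sponsor.

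A reader might also infer that all five rows matter equally in practice. Three are hematologic, and routine counts fall on Days 11-14 with Day 1 repeats only when needed (Section 11.4.2), so a cut during dosing would usually need an unscheduled count. The fifth row only permits a cut. Grade 3 nausea or vomiting is symptom-driven and likelier to be noticed during dosing, although Section 5 reports a maximum of grade 2 at 150 mg/day in the phase I study. The protocol gives no frequency for any of these events.

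The AUC contrast compares means from six patients each, with widely overlapping spread. It describes the dose gap and shows no difference in risk.

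**Conclusion.** The contradiction stands on the text of Section 9.4.3 alone. Four rows order, and one allows, a sequence for which the two stated rules give 150 versus 100 mg/day in the next cycle. It is an internal contradiction that should be fixed, because it concerns dosing after drug-related toxicity and Section 9.5 lets patients continue treatment after the data cut-off.

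It would be tempting to conclude that the conflict decides who enters the primary PFS-3 set, and to rank it as a must-fix on that ground. The documents do not support that. The effect needs a cycle 1 event, a cut starting on Days 2-6, and a criterion counted in mg against full planned drug; Section 12.2 states neither unit nor denominator. The two-stage decision rule and the definition of PFS-3 are unaffected.

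**What to change.** The sponsor should reconcile the no-re-escalation sentence with the Table 4 note, footnote ¶ and the five rows, so that each row yields one next-cycle dose. The reference dose should be written into each row, so that sites need not combine the row with a separate note. If the table is meant to stand, the general sentence has to exempt these rows expressly. If the sentence is meant to stand, the note, the footnote and the next-cycle entries in these rows have to change to agree with it. Which rule stands is for the sponsor to decide.

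The cost is a wording change to Section 9.4.3 and Table 4, by amendment or clarification letter to sites. No procedure, visit or patient is added.

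### Two row definitions in dose-modification Table 4 are wrong, so one haematological event can fit rows that lead to 150 or to 100 mg/day

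*Protocol*

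**What the plan says.** Protocol section 9.4.3, Table 4, lists toxicities in the first column, the action during the cycle in the second and the dose for the next cycle in the third. The first column is headed "Toxicity (Graded as per NCI CTCAE Criteria, Version 3.0".

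**Neutropenia**
- Grade 3 is "Grade 3 Neutropenia (ANC <1000-500/mm"³. The dose is lowered one level if the event occurs during dosing, and the level is maintained for the next cycle.
- Grade 4 has two rows, one for less than 7 days and one for 7 days or more. Both print "Grade 4 Neutropenia (ANC < 1000/mm"³. The shorter one has the same actions as Grade 3. The longer one sits in the block of severe rows.

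**Platelets**
- Grade 3 (25,000 to below 50,000/mm³), "uncomplicated or lasting less than 5 days": lower the dose one level during dosing, maintain the level for the next cycle.
- Grade 3 or higher (below 50,000/mm³), uncomplicated for 5 days or "more, or associated with bleeding and/or" needing transfusion: this also sits in the severe block.

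The severe block ends with "Any other grade 4 hematological toxicity". Its action is "If occurs during treatment, interrupt the treatment", then one dose level down for the next cycle. In the text available for this review, that action is printed only beside the neutropenic infection row. The neighbouring rows have empty action cells, so it is read here as one merged cell for the whole block.

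**The concern.** A dose-modification table should send each event to one row. Here a Grade 4 definition contains the whole Grade 3 range, and a mild platelet row overlaps a severe one. After the same toxicity, two sites could each follow a printed row and restart a patient at different doses.

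The choice carries forward, because section 9.4.3 says that doses reduced for drug-related toxicity should not be raised again unless an exception is discussed with the Sponsor. The platelet overlap includes events with bleeding, where the instruction most needs to be clear. It also affects the action within a cycle: lower the dose and continue, or interrupt.

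**Working it through.** No sample size or error rate is involved. The check writes the rows as rules and looks for cases that match rows with different actions.

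**Neutropenia (next-cycle action)**

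| ANC, duration | As printed (Grade 4 <1000) | With Grade 4 <500 |
|---|---|---|
| 700, 3 days | Grade 3: maintain; Grade 4 under 7 days: maintain (same) | Grade 3: maintain |
| 700, 8 days | Grade 3: maintain; Grade 4 of 7 days or more: down 1 (**conflict**) | Grade 3: maintain |
| 300, 3 days | Grade 4 under 7 days: maintain | unchanged |
| 300, 8 days | Grade 4 of 7 days or more: down 1 | unchanged |

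Conflicts: 1 of 4 as printed, 0 of 4 after the change. The value 500 is the lower bound of the table's own Grade 3 row, so no outside source is needed.

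**Grade 3 platelets (next-cycle action)**

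| Event | As printed (*or*) | With *and* |
|---|---|---|
| Uncomplicated, 3 days | maintain | maintain |
| Uncomplicated, 6 days | maintain and down 1 (**conflict**) | down 1 |
| Bleeding or transfusion, 3 days | maintain and down 1 (**conflict**) | down 1 |
| Bleeding or transfusion, 6 days | down 1 | down 1 |

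Conflicts: 2 of 4 as printed, 0 of 4 after the change, and no case is left without a row. Grade 4 platelets that are uncomplicated and last under 5 days remain covered by "Any other grade 4 hematological toxicity".

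**Size of the difference between the two actions**
- Dose per cycle: 7 × 150 = 1,050 mg against 7 × 100 = 700 mg; 1 − 700/1,050 = 33.3% lower.
- Mean Day 7 AUC in the phase I study (section 3.2.8, Table 1): 25.3 μM·h at 150 mg/day (SD 8.54, n=6) and 19.9 at 100 mg/day (SD 10.5, n=6); 1 − 19.9/25.3 = 21.3% lower. With six patients per group and these SDs, the exposure figure is only indicative.

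**Evaluability.** The primary analysis set requires at least 80% of drug over the first two cycles (section 12.2). A full first cycle and a second cycle at 100 mg/day give (1,050 + 700)/2,100 = 83.3%. A lower second-cycle dose alone therefore does not remove a patient from the set.

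**The case against.** The neutropenia error is visible to a careful reader. The column is graded by CTCAE and each row opens with a grade, so an ANC of 700 is Grade 3 by the row above and never enters a Grade 4 row. Read by label, the conflict count is 0 of 4. This stands as a limit on the practical harm, although the printed cut-off is still wrong.

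For platelets, one can argue that the severe row names exactly the two disputed cases, so a reader would apply the more specific row. That is a plausible reading, but the table does not state it, and the grade label does not help because both rows include Grade 3. The sentence in section 9.4.3 about acting on the most severe toxicity concerns several toxicities, not one toxicity that fits two rows. Bleeding might be counted as a second toxicity, but an uncomplicated event of 5 days or more remains ambiguous.

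The severe action is read from a merged cell, and every conflict depends on that reading. The empty cells beside it support it.

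The consequences are limited:
- Table 4 is worded as recommended. Section 9.4.4 nevertheless makes it the rule for treatment after recovery.
- Section 9.4.4 blocks a new cycle until ANC is at least 1500 and platelets at least 100,000/mm³. This governs when the next cycle starts, not its dose.
- Routine on-treatment counts fall on Days 11–14. Beyond a conditional pre-dose count on Day 1, none is scheduled during dosing, so a conflict over the in-cycle action needs an unscheduled count.
- Section 3.2.7 reports haematological toxicity in some patients only.

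The counts of 1 in 4 and 2 in 4 describe types of event, not patients.

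**Conclusion.** Both definitions are wrong as written. The platelet conjunction is the more serious error, because nothing in the table resolves it: two of the four kinds of Grade 3 event lead to two different doses. The neutropenia cut-off is a numerical slip that creates a conflict only for an ANC of 500–999 lasting 7 days or more, and only for a reader who goes by the number rather than the grade.

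Where a conflict arises, the next-cycle dose differs by 33.3%. Few patients are likely to be affected. The conclusion assumes that the severe-block action applies to every row with an empty action cell. It concerns dosing safety and consistency between sites; no effect on alpha, power or the evaluable set is claimed. It is worth correcting because section 9.5 lets patients still on drug at the 31 May 2017 cut-off continue treatment.

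**What to change.** In Table 4:
1. Change the cut-off in both Grade 4 neutropenia rows to ANC <500/mm³. Leave the row "Febrile neutropenia (ANC <1,000/mm3 and fever of unknown origin" as it is; its limit of 1,000 belongs to a separate definition.
2. In the milder Grade 3 platelet row, replace *or* by *and*, so that it covers only events that are both uncomplicated and shorter than 5 days.

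The cost is two numbers and one word, plus a short clarification letter to sites with patients still on treatment.
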